## 2. Study Objectives and Endpoints

- **Primary Endpoint:**
  - Proportion of MI oocytes maturing to MII within 4 hours of culture.
- **Secondary Endpoints:**
  - Fertilization rate (percentage of matured MII oocytes achieving normal 2PN post-ICSI)
  - Day 3 and blastocyst embryo quality
  - Implantation rate (number of gestational sacs per embryo transferred)
  - Clinical pregnancy rate (confirmed fetal heartbeat at 8–10 weeks)

**3. Sample Size and Power** A total of 60 patients will be enrolled, based on preliminary estimates indicating that this sample size provides >80% power to detect a 25% difference in maturation rates at a two-sided alpha of 0.05, assuming maturation rates improve from ~40% (control) to ~65% (exosome group).

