## 4. Analysis Populations

- **Full Analysis Set (FAS):** All retrieved MI oocytes allocated to either exosome or standard culture conditions.
- **Per Protocol Set (PPS):** Oocytes that completed the planned culture period without protocol deviations.

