## 5. Statistical Methods

- **Primary Analysis:**
  - Compare the proportion of MI oocytes maturing to MII between exosome and standard media using chi-square or Fisher's exact tests.
- **Secondary Analyses:**
  - Compare fertilization rates and embryo quality using similar tests.
  - Implantation and clinical pregnancy rates summarized descriptively and analyzed if numbers permit.
- **Adjustment:** Logistic regression models may adjust for patient age, baseline AMH, and total gonadotropin dose.
- **Significance:** Two-sided tests,  $p<0.05$  considered statistically significant.

**6. Handling of Missing Data** Missing maturation outcomes will be treated conservatively as non-matured. Sensitivity analyses may exclude such oocytes. No imputation planned for secondary reproductive outcomes.

**7. Interim Analyses and Data Monitoring** No formal interim analyses are planned. Data will be reviewed periodically for safety and protocol compliance by the study team.

**8. Reporting Conventions** Descriptive statistics will include means, medians, standard deviations, and ranges. Tables and figures will illustrate maturation rates and embryo development outcomes by intervention.

---

End of Statistical Analysis Plan.

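### Is the >80% power claimed for 60 patients undermined because the primary analysis counts MI oocytes and no oocyte number is given?

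*Combined protocol and SAP*

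**What the plan says.** SAP 3 sets the size in patients: "A total of 60 patients will be enrolled, based on preliminary estimates indicating that this sample size provides >80% power". The effect behind that power is a gain of 25 percentage points, tested two-sided at the 5% level. The assumed maturation rates are about 40% in control and about 65% with exosomes.

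The rest of the plan works in oocytes. The primary endpoint in SAP 2 is "Proportion of MI oocytes maturing to MII within 4 hours of culture". The FAS in SAP 4 is "All retrieved MI oocytes allocated to either exosome or standard culture conditions". SAP 5 plans to "Compare the proportion of MI oocytes maturing to MII between exosome and standard media using chi-square", with Fisher's exact test as the named alternative and no rule for choosing between them. Protocol 3 splits each patient's MI oocytes between the two media, without stating a ratio.

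Two other sections bear on the point. SAP 6 says: "Missing maturation outcomes will be treated conservatively as non-matured". SAP 7 says: "No formal interim analyses are planned. Data will be reviewed periodically for safety and protocol compliance by the study team". No section gives an expected number of MI oocytes, and the entry criteria in Protocol 4 do not require a patient to have one.

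**The concern.** Power for a comparison of oocyte proportions depends on the number of oocytes, and the plan controls only the number of patients. Protocol 1 describes the population as one with few mature oocytes, so a low MI count is easy to imagine. If 60 patients supplied fewer oocytes than the calculation assumed, enrolment would still stop at 60, and SAP 7 contains no rule that would notice. A non-significant result might then be read as evidence against a 25-point effect when the trial had little chance of finding one.

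The reading that best reproduces the claim, one MI oocyte per arm per patient, also seems to leave no slack. Fisher's test falls below 80% there, and counting missing outcomes as non-matured lowers power further.

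**Working it through.** **Inputs.** From SAP 3: 60 patients, rates 0.40 and 0.65, two-sided 0.05. From SAP 5: chi-square or Fisher. From SAP 6: missing counted as non-matured. Assumed, because the documents are silent: MI yield per enrolled patient, a 1:1 split, the missing rate, and independent oocytes unless stated.

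**1. Reproducing the plan's figure.** Take one MI oocyte per arm per patient, so n = 60 per arm. The pooled formula is

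power = Φ{[d√n − 1.96√(2p̄q̄)] / √(p₁q₁ + p₂q₂)}

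with d = 0.25, p̄ = 0.525, q̄ = 0.475:

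- d√n = 0.25 × 7.746 = 1.936
- 1.96 × √0.49875 = 1.384
- √(0.24 + 0.2275) = 0.684
- (1.936 − 1.384)/0.684 = 0.808, and Φ(0.808) = 79.0%

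Full enumeration gives 80.3% for chi-square and 74.7% for Fisher. The formula needs 62 per arm for 80%, or 70 with continuity correction. Read instead as 60 oocytes in total (30 per arm), the pooled formula gives 49.1%, so that reading does not reproduce the claim.

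**2. Dependence on yield.** Oocytes per arm = 60 × yield / 2. Enumerated power with no missing outcomes, and patients needed for 80% power (2 × 60 / yield for chi-square, 2 × 70 / yield for Fisher, rounded up):

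| Assumed MI per patient | Per arm | Power, chi-square / Fisher | Patients for 80%, chi-square / Fisher |
|---|---|---|---|
| 1.0 | 30 | 50.5 / 39.9% | 120 / 140 |
| 1.5 | 45 | 65.4 / 57.3% | 80 / 94 |
| 2.0 | 60 | 80.3 / 74.7% | 60 / 70 |
| 2.5 | 75 | 88.2 / 85.4% | 48 / 56 |
| 3.0 | 90 | 91.8 / 89.4% | 40 / 47 |

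Nothing in the documents favours one row over another.

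**3. Which test.** At 60 per arm the smallest expected cell is 60 × 0.475 = 28.5. An analyst choosing between the two tests in the usual way would use chi-square. In effect-size terms the gap is small: from 40%, the difference detectable with 80% power is 24.9 points by chi-square and 26.5 by Fisher, on rates that SAP 3 itself marks as approximate.

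**4. Missing outcomes.** If 40% and 65% are rates among observed oocytes, a missing fraction m turns them into 0.40(1 − m) and 0.65(1 − m). At m = 5% the rates are 0.38 and 0.6175, a difference of 23.75 points. Power at 60 per arm is then 76.1% (chi-square) or 69.9% (Fisher). At 90 per arm, even m = 10% leaves 85.2% and 81.6%. No missing rate is given, and the outcome is read at 2, 3 and 4 hours of culture (Protocol 5), so a rate of 5 to 10% is purely an assumption.

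**5. Within-patient correlation.** With one oocyte per arm per patient, the variance of the difference is [0.24 + 0.2275 − 2ρ√(0.24 × 0.2275)]/n. At ρ = 0.2 the bracket falls from 0.4675 to 0.4675 − 0.4 × 0.2337 = 0.3740. Positive correlation therefore helps. Simulation at 60 per arm with ρ from 0.1 to 0.3 gives 81.6 to 84.6% for chi-square and 75.9 to 78.6% for Fisher. With 5% missing, chi-square is 77.3 to 80.0%. Independence is thus the unfavourable assumption at this yield.

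**The case for a change.** The strongest case is that the gap is certain even though its size is not. The stated power cannot be checked from the plan, and it runs from 50.5% to 91.8% (chi-square) over yields of 1 to 3. On the reading that reproduces the claim, small losses matter: one missing outcome per arm gives 78.9% (chi-square) or 73.1% (Fisher), and two patients with no MI oocyte (58 per arm) give 78.0% or 72.0%. Fisher is named and stays below 80% across the correlations considered. Counting allocated oocytes uses no outcome data and costs no alpha, so a target in oocytes looks cheap.

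Part of this stands. The yield is unreported, the choice of test is left open, and the power statement is conditional on a count the reader does not have.

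The rest does not carry a change. The lack of margin is a property of a yield picked because it lands on 80%; at 2.5 per patient both tests exceed 85%. Movements of one or two points around 80% mean little when the input rates are approximate. SAP 7 does not prevent the team from counting oocytes or from asking to extend enrolment, because a count of allocated oocytes is not an interim analysis. Nor is a recruitment rule in oocytes cheap. At yields of 1.0 to 1.5 it asks for 80 to 140 patients. At 3.0 it could stop at 40 (chi-square), leaving fewer patients for implantation and clinical pregnancy.

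**Conclusion.** The concern identifies missing detail, not an error. The >80% figure is reproduced by exact chi-square at 60 MI oocytes per arm with complete data and independent oocytes (80.3%; pooled formula 79.0%). Higher yields exceed it and lower yields miss it, and the documents do not say which applies. Under-powering is therefore not shown, and 60 patients may be too few or more than enough.

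Reporting the yield, the oocytes per arm and the test used for sizing would make the statement checkable. It would not alter who is enrolled, how oocytes are allocated or how the primary comparison is made. An analyst can fill these gaps sensibly: chi-square where expected cells are near 28, and a running count of allocated oocytes kept without outcome data. At the end, the FAS denominators show the oocyte number actually reached, and a non-significant result should be read against that number rather than against the planned power. Recruiting to an oocyte count remains an option for the sponsor, but with real costs in both directions and no stated figure shown to be missed, the plan need not change on this point.

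This conclusion rests on a 1:1 split and on assumed yields, missing rates and correlations; none of these is in the documents.

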## 4. Analysis Populations

- **Full Analysis Set (FAS):** All retrieved MI oocytes allocated to either exosome or standard culture conditions.
- **Per Protocol Set (PPS):** Oocytes that completed the planned culture period without protocol deviations.

## 5. Statistical Methods

- **Primary Analysis:**
  - Compare the proportion of MI oocytes maturing to MII between exosome and standard media using chi-square or Fisher's exact tests.
- **Secondary Analyses:**
  - Compare fertilization rates and embryo quality using similar tests.
  - Implantation and clinical pregnancy rates summarized descriptively and analyzed if numbers permit.
- **Adjustment:** Logistic regression models may adjust for patient age, baseline AMH, and total gonadotropin dose.
- **Significance:** Two-sided tests,  $p<0.05$  considered statistically significant.

**6. Handling of Missing Data** Missing maturation outcomes will be treated conservatively as non-matured. Sensitivity analyses may exclude such oocytes. No imputation planned for secondary reproductive outcomes.

**7. Interim Analyses and Data Monitoring** No formal interim analyses are planned. Data will be reviewed periodically for safety and protocol compliance by the study team.

**8. Reporting Conventions** Descriptive statistics will include means, medians, standard deviations, and ranges. Tables and figures will illustrate maturation rates and embryo development outcomes by intervention.

---

End of Statistical Analysis Plan.

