## 2. Objectives

- **Primary Objective:** To determine if exosome-enriched culture media increases the proportion of MI oocytes maturing to MII within 4 hours compared to standard IVF media.

- **Secondary Objectives:** To assess subsequent fertilization rates, embryo quality, blastocyst development, implantation, and clinical pregnancy rates.

**3. Study Design** A prospective, single-center, randomized controlled trial. Patients will undergo standard ovarian stimulation protocols. Retrieved MI oocytes will be allocated within each patient to two different culture conditions: exosome-enriched media vs. standard media.

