## 6. Outcome Measures

- **Primary Outcome:** Proportion of MI oocytes achieving MII maturation within 4 hours.
- **Secondary Outcomes:** Fertilization rates, day 3 embryo quality, day 5 blastocyst quality, implantation rate, and clinical pregnancy rate.

**7. Statistical Considerations** Categorical outcomes will be compared using chi-square or Fisher's exact tests. Logistic regression will adjust for

patient age, AMH, and gonadotropin dose. A p-value  $<0.05$  will be considered statistically significant.

**8. Ethical Considerations** The study will adhere to the Declaration of Helsinki and Good Clinical Practice guidelines. Ethical approval will be obtained prior to enrollment. All participants will provide written informed consent. Confidentiality will be maintained, with data anonymized using unique study codes.

**9. Data Handling and Confidentiality** Data will be stored in secure, password-protected systems. No personally identifiable information will be shared or published.

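### The primary test treats sibling MI oocytes, divided between both media within each patient, as independent samples, so the nominal 5% level is not assured

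*Combined protocol and SAP*

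**What the plan says.** - Protocol 3 (Study Design): "Retrieved MI oocytes will be allocated within each patient to two different culture conditions". Neither document gives a split ratio, a rule for odd counts or a rule for a patient with a single MI oocyte.
- SAP 4 (Analysis Populations) makes the oocyte the unit of analysis: "All retrieved MI oocytes allocated to either exosome or standard culture conditions".
- SAP 5, primary analysis: "Compare the proportion of MI oocytes maturing to MII between exosome and standard media using chi-square or Fisher's exact tests". Protocol 7 agrees: "Categorical outcomes will be compared using chi-square or Fisher's exact tests".
- SAP 5, adjustment: "Logistic regression models may adjust for patient age, baseline AMH, and total gonadotropin dose". Protocol 7 words this adjustment as definite, whereas the SAP makes it optional. All three covariates describe the patient.
- SAP 5, secondary analyses: "Compare fertilization rates and embryo quality using similar tests".
- SAP 3 enrols 60 patients and states that "this sample size provides >80% power to detect a 25% difference in maturation rates at a two-sided alpha of 0.05", for about 40% against about 65%. It does not give the number of MI oocytes.

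Pairing, stratification by patient, random effects, GEE, clustered variance and sibling correlation appear nowhere in either document.

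**The concern.** Oocytes from one woman share her age, ovarian biology and stimulation cycle, so their outcomes are likely to be correlated. Dividing them between media can use that correlation to sharpen the comparison, but only if the analysis recognises the patient. A chi-square or Fisher test on the pooled two-by-two table uses the variance of two independent samples, which is not the variance this design produces.

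Adjusting for age, AMH and gonadotropin dose does not repair this. Those values are the same for all of a woman's oocytes and leave the remaining sibling correlation unmodelled.

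At stake are the p-value of the only primary test, any confidence interval based on the same variance, and the secondary comparisons that reuse these tests.

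**Working it through.** **Inputs from the documents:** 60 patients, rates 0.40 and 0.65, two-sided alpha 0.05 (SAP 3); within-patient allocation (Protocol 3). **Assumed, because the documents give none:** correlations, MI counts per patient, split rule.

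**1. The plan's own power figure.** Take 60 patients to mean 60 independent oocytes per medium. With d = 0.25 and mean rate 0.525:
- null SE = √(2 × 0.525 × 0.475 / 60) = 0.0912
- alternative SE = √((0.40 × 0.60 + 0.65 × 0.35) / 60) = 0.0883
- power = Φ((0.25 − 1.96 × 0.0912) / 0.0883) = 79.0%

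The unpooled formula gives 80.9%, exact chi-square 80.3% and Fisher 74.7%. With 30 per arm, power is 49.1%. So the stated figure appears, to within about a point for chi-square, only if pairing and MI counts are ignored.

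**2. True level of the pooled test, even split.** Let each patient supply m oocytes per medium, with correlation r_w within a medium and r_a across media (binary scale). The true variance of the difference is the assumed variance times

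F = 1 + (m − 1) r_w − m r_a,

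and the true level is 2 × (1 − Φ(1.96 / √F)).

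| Case | F | True level |
|---|---|---|
| r_w = r_a = 0.2, any m | 0.8 | 2.8% |
| r_w = r_a = 0.3, any m | 0.7 | 1.9% |
| r_w = r_a = 0.4, any m | 0.6 | 1.1% |
| m = 2, r_w = 0.3, r_a = 0.1 | 1.1 | 6.2% |
| m = 2, r_w = 0.3, r_a = 0 | 1.3 | 8.6% |
| m = 3, r_w = 0.3, r_a = 0 | 1.6 | 12.1% |

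With m = 1, F = 1 − r_a, so non-negative correlation cannot inflate the level. Higher correlation within a medium could arise if siblings share a well. Protocol 5 doses exosomes per well but does not say how many oocytes a well holds.

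**3. Simulation** (60 patients, null rate 40%, latent probit model). Correlations here are on the latent scale. At a 40% rate, latent 0.3 is about 0.19 on the binary scale and latent 0.5 about 0.33, so they should not be read against the table above. Mixed counts means 25/35/25/15% of patients with 1/2/3/4 MI oocytes. Ranges cover repeated runs or several cases.

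| Case | Chi-square level |
|---|---|
| Mixed counts, split as evenly as possible, correlation 0.3 | 3.2–3.3% |
| Same, correlation 0.5 | 2.3% |
| Same, 0.375 within and 0.125 across media | 5.2–5.4% |
| Two per medium, 0.375 / 0.125 | 6.0–6.6% |
| Four per medium, 0.375 / 0.125 | 9.1–9.6% |
| Each oocyte randomised separately, patient effect only | 4.9–5.3% |
| Each oocyte randomised separately, 0.375 / 0.125 | 6.0–8.0% |

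A patient-level robust test of the risk difference (t on 59 df) stayed between 4.8% and 5.6% throughout.

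**4. A patient term alone may not suffice.** At 0.375 / 0.125, a random-intercept logistic model gave 8.6% (two per medium) and 12.6% (four per medium), against 5.3% and 5.0% for robust inference. In a separate beta-binomial simulation with correlation 0.3 within a medium, no patient effect and two per medium, a Cochran-Mantel-Haenszel test stratified by patient gave 10.2%.

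**5. Power with one oocyte per medium per patient.** The discordant share is pd = 0.40 + 0.65 − 2 × (0.26 + r × √(0.24 × 0.2275)). McNemar power is Φ((√n × 0.25 − 1.96 × √pd) / √(pd − 0.0625)).

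| r (binary scale) | pd | n = 60 | n = 45 |
|---|---|---|---|
| 0 | 0.530 | 77.2% | 64.3% |
| 0.2 | 0.437 | 85.3% | 73.4% |
| 0.3 | 0.390 | 89.4% | 78.6% |
| 0.4 | 0.343 | 93.2% | 84.1% |

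For 60 pairs at r = 0.3, the planned chi-square has power Φ((0.25 − 1.96 × 0.0912) / √((0.390 − 0.0625) / 60)), about 83%, against 89% for McNemar.

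**The case against.** The best defence is that the natural reading of Protocol 3 is a roughly even split with a shared patient effect. The test is then conservative, so a positive result would stand. Inflation needs several oocytes per medium, or separate randomisation of each oocyte, together with extra correlation within a medium. Poor responders may have few MI oocytes. With the mixed counts split evenly, the inflating correlation gives only 5.2–5.4%.

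The power cost is also modest. On the mixed counts, chi-square has 86% and 88% power at latent 0.3 and 0.5, a loss of about 3 and 5 points against the robust test. The 45-pair McNemar figures discard single-oocyte patients, whom a GEE keeps. Robust-test power on the mixed counts is 83–93%.

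These points stand, and they rule out any claim that false positives are certainly inflated or that power is certainly short. They do not rescue the test. The defence rests on an even split and a correlation pattern that the documents never state. With separate randomisation of the mixed counts, the level at 0.375 / 0.125 is 6.6%. Even in the favourable case, the p-value and any matching interval do not have their nominal properties.

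**Conclusion.** The concern holds. The primary test does not match the within-patient allocation, and that mismatch can be read directly from the documents with high confidence. The size and direction of the error cannot. On the assumed inputs above, the true level runs from 1.1% to 12.1%, and several plausible cases lie close to 5%. The conclusion is that the 5% level is not assured, not that it is exceeded.

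The power claim in SAP 3 does not say which analysis or how many MI oocytes it assumes. It must be fixed before outcomes are known, because the main result of the trial rests on this one test.

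**What to change.** - **Primary test (SAP 5, Protocol 7).** Name one analysis whose p-value and 95% confidence interval both come from patient-level inference. An example is a GEE or marginal logistic model with a treatment effect, patient as cluster and small-sample-corrected robust variance, reporting the risk difference. It keeps patients with a single MI oocyte. If a mixed model is preferred, include a patient-by-treatment random effect as well as the intercept. Keep chi-square or Fisher for description only.
- **Adjusted model.** Use the same clustering, and make the two documents agree on whether it will be fitted.
- **Fertilization and embryo quality.** Apply the same clustering.
- **Allocation (Protocol 3).** State how oocytes are split, including odd counts and single MI oocytes, and whether siblings share a well.
- **Power (SAP 3).** Restate it for the chosen analysis, with the assumed MI counts and correlation.

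The cost is wording in these four sections and slightly more modelling. The change of test needs no extra patients or data. The restated power may fall below 80% if many patients have only one MI oocyte, although it did not at the 25% share assumed above.

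### Embryo quality is assigned chi-square or Fisher's exact tests with no grading scale defined: order is ignored if grades are kept, and a good/poor split has no pre-specified cut-off

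*Combined protocol and SAP*

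**What the plan says.** SAP section 2 lists "Day 3 and blastocyst embryo quality" among the secondary endpoints, and protocol section 6 lists "day 3 embryo quality, day 5 blastocyst quality". Neither gives a scale, a number of grades or a good/poor cut-off.

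The SAP's only analysis statement for this endpoint is in section 5: "Compare fertilization rates and embryo quality using similar tests". The line above it compares the primary endpoint "between exosome and standard media using chi-square or Fisher's exact tests", so that is what the tests are similar to. Protocol section 7 has the same general rule: "Categorical outcomes will be compared using chi-square or Fisher's exact tests".

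No rank, trend or ordinal method appears in either document. The SAP's regression is optional ("Logistic regression models may adjust for patient age, baseline AMH, and total gonadotropin dose"), is not described as ordinal, and is not tied to particular outcomes. The sample-size statement (SAP section 3) concerns maturation only.

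**The concern.** Quality means better or worse, so any scale with three or more grades has an order. A chi-square or Fisher test on a grades-by-medium table treats the grades as labels, and permuting the grade columns leaves the p-value unchanged. Two things follow if grades are kept:

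- The test spreads its degrees of freedom over patterns that are neither better nor worse, so it has less power against a shift towards better embryos.
- It can be significant when one medium yields more of both the best and the worst embryos.

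Collapsing to good/poor avoids both problems but discards grade information. With no cut-off stated, the split could be chosen after the data are seen. The number of embryos is likely to be small, so efficiency matters.

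**Working it through.** **The plan's own figure.** No power is stated for embryo quality. The only stated power, above 80%, is for maturation at 40% vs 65%. Reading the 60 patients as 60 independent oocytes per medium:

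- Pooled: z = [0.25 − 1.96·√(2·0.525·0.475/60)] / √((0.24 + 0.2275)/60) = (0.25 − 0.1787)/0.0883 = 0.81, power 0.790.
- Unpooled: z = 0.25/0.0883 − 1.96 = 0.87, power 0.808.

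The figure is roughly reproduced on that reading. Nothing below changes it.

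**Inputs for embryo quality.** From the documents: the choice of test, two-sided alpha 0.05, and the 40% and 65% maturation rates. Assumed, because the documents are silent: number of grades, grade distribution, size of effect, embryo counts. The smallest count takes one oocyte per medium per patient and 70% normal fertilization: 60 × 0.40 × 0.70 ≈ 17 and 60 × 0.65 × 0.70 ≈ 27.

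**Model.** For every grade j, odds(grade ≥ j | exosome) = OR × odds(grade ≥ j | standard). For example, four equal control grades with OR 2 become 0.14, 0.19, 0.27, 0.40.

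**Power, grades kept or split.** 20,000 runs per row, independent embryos, equal control grades:

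| Grades | OR | Embryos | k×2 chi-square | Good/poor 2×2 | Wilcoxon |
|---|---|---|---|---|---|
| 3 | 2 | 17/27 | 0.176 | 0.185 | 0.224 |
| 3 | 2 | 60/60 | 0.429 | 0.388 | 0.534 |
| 4 | 2 | 17/27 | 0.159 | 0.202 | 0.235 |
| 4 | 2 | 60/60 | 0.388 | 0.465 | 0.551 |
| 4 | 3 | 17/27 | 0.342 | 0.417 | 0.486 |
| 4 | 3 | 60/60 | 0.791 | 0.817 | 0.908 |
| 5 | 2 | 17/27 | 0.138 | 0.204 | 0.236 |
| 5 | 2 | 60/60 | 0.352 | 0.420 | 0.563 |

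The k×2 chi-square loses from 0.224 − 0.176 ≈ 5 points to 0.563 − 0.352 ≈ 21 points against the rank test. Under no effect all three tests reject about 5% of the time.

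A second set of runs (6,000 each) used four grades with control distribution 15/35/30/20%. Power for chi-square, split and rank test:

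- OR 4, 17 vs 27: 49%, 57%, 66%.
- OR 4, 30 vs 30: 66%, 69%, 82%.
- OR 2.5, 30 vs 30: 32%, 40%, 48%.

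With four grades cut in the middle, the split's loss against the rank test runs from about 3 points (0.235 − 0.202) to about 13 (82% − 69%). With three or five grades the cut used was off-centre. The loss then started from a similar 3 to 4 points and reached about 20 (three grades, OR 3, 28 vs 45: 0.677 − 0.480), so the position of the cut matters.

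**Direction.** Take grades 4/11/11/4 against 11/4/4/11. Each column totals 15, so every expected count is 7.5 and every deviation is 3.5. Chi-square = 8 × 3.5²/7.5 = 13.07 on 3 df, p = 0.0045. The rank test gives p = 1.0. In simulation, 25% in each grade against 40/10/10/40% made chi-square significant in 61% of runs (28 vs 45) and 85% (60 vs 60). Wilcoxon was significant in about 4% and 6%.

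**Does the gain survive within-patient allocation?** A patient-clustered ordinal score test was simulated for 60 patients with one or two oocytes per medium, with and without within-patient correlation. It held about 4 to 5% type I error. It beat the 4×2 chi-square by about 8 to 16 points and the good/poor split by about 3 to 12 points, at OR 2.5 and 4.

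A patient-stratified Cochran-Mantel-Haenszel row-mean-score test does not keep the gain. With one oocyte per medium, about 60 × (0.40 × 0.70) × (0.65 × 0.70) ≈ 8 patients have an embryo in both media, and only they contribute. Its simulated power (4,000 runs, no within-patient correlation) was 21% at OR 4, against 49% for chi-square. At OR 2.5 it was 11% against 24%.

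**The case against.** The strongest reply is that the documents never say quality is graded on an ordered scale, or that grades are recorded. Embryo quality shares a sentence with the fertilization rate, so a good-quality proportion is a natural reading. A 2×2 test is then valid and its direction is plain. This stands, and it is why the point is conditional. It does not remove the need for an edit, because on that reading the cut-off is missing and some power is still given up.

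A reader might infer that a significant chi-square is likely to favour the wrong medium. The calculations do not support that. Under a true proportional-odds improvement, a significant result not favouring exosomes occurred in 0.3% of runs or fewer. The direction problem is confined to mixed patterns over three or more grades. A two-sided rank p-value does not state direction either; the estimate and the table do, and SAP section 8 already promises tables and figures by intervention.

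It is also fair that no test rescues a very small sample. At OR 2 with 17 vs 27 embryos, even the rank test has power of only 22 to 24%.

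Finally, a reader might take the official title to make embryo development a co-equal question. The sole primary endpoint is maturation, and embryo quality is one of several secondary endpoints.

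**Conclusion.** The point holds conditionally. If three or more ordered grades are kept, the planned tests lose about 5 to 21 points of power against an ordered test and can be significant without a net shift to better embryos. If quality is split good/poor, the test is sound but loses about 3 to 13 points with four grades cut in the middle (more with some off-centre cuts), and the cut-off is left open. These sizes rest on assumed grade distributions, odds ratios and embryo counts. The rank-test comparisons treat embryos as independent; only the clustered check allows for within-patient correlation.

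The documents do not support a claim that the planned tests are invalid on this ground, since the simulated type I error was about 5% throughout. Nor do they support treating ordered, recorded grades as a fact of the plan. That chi-square and Fisher tests ignore several oocytes coming from one patient is a separate matter. This is a worthwhile, low-cost improvement to an endpoint with no stated power, and it does not bear on the primary analysis.

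**What to change.** In SAP sections 2 and 5, before data are analysed:

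- Name the day 3 and blastocyst grading scales and list their ordered categories.
- Analyse each grade with a proportional-odds (ordinal logistic) model on medium, with standard errors clustered on patient. Report the common odds ratio with 95% CI beside the full grade table.
- Keep chi-square or Fisher-type comparisons for yes/no outcomes only. If a good-quality proportion is preferred, state the cut-off now.
- Do not make the patient-stratified row-mean-score test the main analysis, because its power could fall below that of the current test.

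The cost is SAP wording and a few lines of code, plus grade-level recording if that is not already intended. The downside is small: one common odds ratio summarises the shift and relies on approximately proportional odds, which is why the full table should accompany it.

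### Implantation and clinical pregnancy may be tested between media, although no patient or transfer is randomized to a medium and no rule ties a sac or pregnancy to one

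*Combined protocol and SAP*

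**What the plan says.** Protocol section 3 sets the unit of allocation: "Retrieved MI oocytes will be allocated within each patient to two different culture conditions". SAP section 4 follows it. The Full Analysis Set is "All retrieved MI oocytes allocated to either exosome or standard culture conditions", and the Per Protocol Set also consists of oocytes. No patient, transfer or embryo set is defined.

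SAP section 2 lists two secondary endpoints that arise after transfer. Implantation is counted as sacs per transferred embryo. Clinical pregnancy is a fetal heartbeat at 8–10 weeks, with no denominator given. Neither definition mentions the medium in which the oocyte was cultured.

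On analysis, SAP section 5 says: "Implantation and clinical pregnancy rates summarized descriptively and analyzed if numbers permit". Protocol section 7 gives a general rule with no exemption: "Categorical outcomes will be compared using chi-square or Fisher's exact tests". The SAP sets two-sided p<0.05 as the criterion for significance.

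Neither document says how embryos are chosen for transfer, how many are transferred, whether embryos from both media may go into one transfer, or whether embryos from oocytes already mature at retrieval may be transferred.

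**The concern.** A patient whose oocytes are split is exposed to both media, so her pregnancy belongs to no randomized arm. A between-media test could be built in two ways. One counts the same patient in both arms, which breaks the independence that a chi-square or Fisher test needs. The other groups patients by the source of the transferred embryo, which is settled after allocation.

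Sample size is the only obstacle the SAP recognizes, but more data would not supply a randomized group or an attribution rule. At stake is a nominal p-value on clinical pregnancy, which readers could take as a randomized effect of exosomes when it may only reflect which patients had an embryo from each arm.

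**Working it through.** **The plan's own figure.** The only power statement (SAP section 3) concerns maturation: 60 patients, more than 80% power, 40% against 65%, two-sided 0.05. With pooled variance, the number per group for 80% power is

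n = [1.960·√(2·0.525·0.475) + 0.842·√(0.40·0.60 + 0.65·0.35)]² / 0.25² = 61.4, so 62.

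Sixty oocytes per medium give 79.0% power, so the figure is roughly reproduced if 60 patients means 60 oocytes in each medium. No rate, effect or power is stated for implantation or pregnancy, so there is nothing to reproduce for those outcomes.

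**Is there a randomized group for these outcomes?**

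| Step | What is fixed by allocation | What is decided later |
|---|---|---|
| MI oocyte placed in a medium | Medium | – |
| Matured MII oocyte | – | Depends on medium (the primary hypothesis) |
| Embryo available | – | Depends on maturation, fertilization and development |
| Embryo transferred | – | Choice among available embryos; no rule given |
| Sac or pregnancy | – | One patient, possibly with embryos from both media |

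Randomization protects the first row only. A transfer whose embryos all come from one arm can be traced to its medium, but membership of that group is a result of the later rows. In a mixed transfer where only some embryos implant, a sac cannot be assigned from the stated data.

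**How uneven could the later grouping be?** Inputs from SAP section 3: maturation 0.65 (exosome) and 0.40 (standard). Assumptions, because the documents do not give them: m = 1, 2 or 3 MI oocytes per arm per patient, equal numbers in both arms, independent oocytes, and no fertilization or transfer losses yet.

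Chance of at least one matured oocyte: a = 1 − 0.35^m (exosome), b = 1 − 0.60^m (standard).

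Exosome only = a(1 − b); standard only = (1 − a)b; both = ab; neither = (1 − a)(1 − b).

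| m | a | b | Exosome only | Standard only | Both | Neither | Ratio exosome only : standard only |
|---|---|---|---|---|---|---|---|
| 1 | 0.650 | 0.400 | 0.390 | 0.140 | 0.260 | 0.210 | 2.79 |
| 2 | 0.878 | 0.640 | 0.316 | 0.078 | 0.562 | 0.044 | 4.03 |
| 3 | 0.957 | 0.784 | 0.207 | 0.034 | 0.750 | 0.009 | 6.15 |

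If all 60 patients had the given count, the expected single-source patients would be 23.4 against 8.4 (m = 1), 19.0 against 4.7 (m = 2) and 12.4 against 2.0 (m = 3).

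**Sensitivity to within-patient correlation.** Give each patient a standard normal effect u and set the maturation probability to Φ((Φ⁻¹(p) + √0.3·u)/√0.7). This keeps the marginal rates at 0.65 and 0.40 with a latent intraclass correlation of 0.3, which is also an assumption. Averaging over u gives ratios of 3.57, 5.15 and 6.82 for m = 1, 2 and 3, with both arms represented in 0.303, 0.536 and 0.670 of patients.

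**The case against.** The strongest objection is that the SAP never says these outcomes will be compared between media. For maturation, fertilization and embryo quality it speaks of comparing; for implantation and pregnancy it changes to description plus an unspecified analysis, and its specific line can be read as overriding the protocol's general rule. It is true that the default is descriptive and that the test is inferred. But the media contrast is the trial's only comparison, the protocol's rule exempts nothing, and analysis set apart from description must mean something more than description. The plan permits the test; it does not require it.

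Second, the ratios do not measure bias. Unequal group sizes alone do not distort a rate per embryo; bias needs the groups to differ in prognosis, and the calculation has no prognosis term. The upper end also needs six MI oocytes per patient, in poor responders. Both points stand: the figures illustrate a split that follows from the hypothesized treatment effect and nothing more.

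Third, fertilization rate and embryo quality also depend on maturation, and this point leaves them alone. That is fair, but those outcomes can be observed on an individual oocyte or embryo of known medium. Here there is the added problem that a pregnancy belongs to a patient exposed to both media.

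Fourth, an attribution rule, or sacs counted per allocated oocyte, might rescue a comparison. The latter does keep the allocated denominator. The choice of which embryo to transfer would still drive the result, and mixed transfers would remain unresolved.

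**Conclusion.** The concern holds. The plan permits a test of two outcomes for which it has no randomized groups, no suitable analysis set and no attribution rule, and the condition it attaches, sufficient numbers, does not address any of these. This conclusion follows from the text and needs no assumed figures.

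The size of the later split does rest on assumptions. With 1 to 3 MI oocytes per arm, single-source patients would be exosome rather than standard by a factor of 2.8 to 6.2 under independence, or 3.6 to 6.8 with a latent correlation of 0.3. Both arms would offer a matured oocyte in 26% to 75% of patients under independence, so a mixed transfer or a choice between arms would be possible. The resulting bias in implantation or pregnancy rates cannot be computed from the documents.

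The effect is confined to two secondary outcomes that are descriptive by default; the primary endpoint is untouched. It should be corrected, as the fault is structural and cheap to remove.

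**What to change.** - **SAP section 5:** delete the clause that allows analysis of implantation and clinical pregnancy when numbers suffice. State that both are reported descriptively, with no between-arm hypothesis test.
- **Protocol section 7:** exempt these two outcomes from the general chi-square/Fisher rule, so that the two documents agree.
- **Data collection:** record the origin of every transferred embryo as exosome MI, standard MI, or mature at retrieval.
- **Reporting:** give clinical pregnancy per patient for the whole cohort. Show implantation by arm only for transfers whose embryos all come from one arm, labelled as a non-randomized description.

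The cost is wording in two places and one data field. Two nominal secondary comparisons are given up. The field should be in place from the first transfer, because origin may not be recoverable later.
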